### **3.5.2. Laboratory Data**

Safety laboratory tests will be performed as described in the protocol.

To determine if there are any clinically significant laboratory abnormalities, the haematological, clinical chemistry (serum) and urinalysis safety tests will be assessed against the criteria specified in the sponsor reporting standards. Post-baseline assessments will not take into account whether each subject’s *baseline* test result is within or outside the laboratory reference range for the particular laboratory parameter.

***Baseline is defined*** as the time-matched data obtained while on placebo [Part 1], 0H assessment on Day 1 [Part 2], ***or*** closest to 0H assessment prior to dosing on Day 1 in ***each*** Period [Part 3]. Results from only the planned study visits will be considered for baseline assessment.

### **3.5.3. Vital Signs**

Single supine blood pressure and pulse measurements will be taken at all time points listed in the Schedule of Activities given in the protocol. ***Baseline is defined*** as the time-matched data obtained while on placebo [Part 1], 0H assessment on Day 1 [Part 2], ***or*** 0H assessment on Day 1 in ***each*** Period [Part 3].

The following vital signs endpoints will be determined for each subject:

- The maximum decrease and increase from baseline over all measurements taken postdose for systolic and diastolic blood pressures.
- The maximum increase from baseline over all measurements taken postdose for pulse rate.

The maximum increase from baseline will be calculated by first subtracting the baseline value from each postdose measurement to give the change from baseline. The maximum of these values over the respective period (Part 1 and Part 3) or entire study (Part 2) will then be selected, except in the case where a subject does not show an increase. In such an instance, the minimum decrease should be taken. Similarly, the maximum

decrease from baseline will be determined by selecting the largest negative value of the changes from baseline.

In cases where a subject does not show a decrease, the minimum increase should be taken.

### 3.5.4. ECG

Single and triplicate 12-lead ECGs will be obtained on all subjects at times detailed in the Schedule of Activities given in the protocol. The average of the triplicate readings collected at each assessment time will be calculated for each ECG parameter. **Baseline is defined** as the average of the time-matched triplicate data obtained while on placebo [Part 1], the average of the triplicate collected at 0H assessment prior to dosing on Day 1 [Part 2], or the 0H predose assessment on Day 1 in each Period [Part 3].

The QT, QTcF, PR, QRS and heart rate will be recorded at each assessment time.

[figure not shown]
If not supplied, QTcF will be derived using Fridericia's heart rate correction formula:

$$\text{QTcF} = \text{QT} / (\text{RR})^{1/3} \quad \text{where RR} = 60/\text{HR} \text{ (if not provided)}$$

The maximum absolute value (postdose) and the maximum increase from baseline for QTcF, PR and QRS, will be determined over all measurements for each subject.

The maximum increase from baseline will be calculated by firstly subtracting the baseline value from each postdose measurement to give the change from baseline. The maximum of these values over the respective period (Part 1 and Part 3) or entire study (Part 2) will then be selected, except in the case where a subject does not show an increase. In such an instance, the minimum decrease should be taken.

CCI

The figure consists of 12 horizontal bars, each composed of a thick black segment and a thin white segment. The black segments are of varying lengths, starting from a very long one at the top and becoming progressively shorter as they descend. The white segments are consistently short, appearing as small gaps or breaks in the black bars. The bars are arranged vertically, with the first bar at the top and the last bar at the bottom. The overall pattern creates a sense of descending or decreasing values.

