8.2.2. Vital Signs

In this study, assessment of vital signs (including BP and pulse rate) will occur at the nominal timepoints specified in the [SoA-Table A](#), [SoA-Table B](#), [SoA-Table C](#), and [SoA-Table D](#) per the following specifications:

- **Single, supine BP and pulse rate** will be measured with the participant's arm supported at the level of the heart, and recorded to the nearest mm Hg after **≥5 minute** of rest;
- The same arm (preferably the dominant arm) will be used throughout the study;

- Participants should be instructed *not* to speak during measurements.

The same properly sized and calibrated BP cuff will be used to measure BP each time. The use of an automated device for measuring BP and pulse rate is acceptable; however, when done manually, pulse rate will be measured in the brachial/radial artery for **at least 30 seconds**. When the timing of these measurements coincides with a blood collection, BP and pulse rate should be obtained prior to the nominal time of the blood collection.

Additional collection times, or changes to collection times, of BP and pulse rate will be permitted, as necessary, to ensure appropriate collection of safety data.

8.2.3. 12-lead ECGs

Standard 12-lead ECGs utilizing limb leads (with a 10-second rhythm strip) should be collected at times specified in [SoA-Table A](#), [SoA-Table B](#), [SoA-Table C](#), and [SoA-Table D](#) using an ECG machine that automatically calculates the HR and measures PR, QT, and QTcF intervals and QRS complex. Alternative lead placement methodology using torso leads (eg, Mason-Likar) is not recommended given the potential risk of discrepancies with ECGs acquired using standard limb lead placement. All scheduled ECGs should be performed after the participant has rested quietly for **≥10 minutes** in a *supine position*.

In Part 1, during conduct of the study: *Triplet* 12-lead ECGs will be obtained approximately 2 to 4 minutes apart; the average of the triplicate ECG measurements collected before dose administration on Day 1 of each period will serve as each participant's baseline QTcF value;

- However, ***for purposes of the CSR***, within-participant, time-matched assessment of each PF-07202954 dose relative to placebo, will be reported.

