When more than 1 ECG is collected at a nominal time after dose administration (for example, triplicate ECGs), the mean of the replicate measurements will be used to represent a single observation at that timepoint. If any of the 3 individual ECG tracings has a QTcF value >500 msec, but the mean of the triplicates is not >500 msec, the data from the participant's individual tracing will be described in a safety section of the CSR in order to place the >500 msec value in appropriate clinical context. However, values from individual tracings within triplicate measurements that are >500 msec will not be included in the categorical analysis unless the average from the triplicate measurements is also >500 msec. Changes from baseline will be defined as the change between the post dose QTcF value and the average of the time-matched baseline triplicate values while on Placebo (in Part 1), the average of the triplicate collected at 0H prior to dosing on Day 1 (in Part 2), **or** the predose value on Day 1 in each Period (in Part 3).

In addition, an attempt will be made to explore and characterize the relationship between plasma concentration and QT interval length using a PK/PD modeling approach. If a PK/PD relationship is found, the impact of participant factors (covariates) on the relationship will be examined.

CCI

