#### **6.6.3. Vital Signs**

##### **Parts 1 and 2 only**

Absolute values and changes from baseline in supine systolic and diastolic blood pressure and pulse rate will be summarized by treatment and time postdose, according to sponsor reporting standards. Tables will be paged by parameter. Baseline is as defined in Section 3.5.3.

Mean changes from baseline for supine systolic and diastolic blood pressure and pulse rate will be plotted against time postdoses. On each plot, there will be 1 line for each treatment, all treatments on the same plot including the placebo. Corresponding individual plots of changes from baseline will also be produced for each treatment.

For supine systolic and diastolic blood pressure and pulse rate, the differences between each dose and placebo (dose – placebo) will be summarized (N, mean, 90% CI) and plotted (mean) for each dose and time postdose (including baseline).

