##### **Parts 1, 2 and 3 (if conducted)**

Maximum absolute values and changes from baseline for vital signs will be summarized descriptively by treatment using categories as defined in Appendix 1. Numbers and percentages of subjects meeting the categorical criteria will be provided. All planned and unplanned postdose timepoints will be counted in these categorical summaries. All values meeting the criteria of potential clinical concern will be listed.

Maximum increase or decrease in vital signs will also be summarized; all planned and unplanned postdose timepoints will be included in these summaries.

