#### **6.6.4. Electrocardiograms**

##### **Parts 1 and 2 only**

Absolute values and changes from baseline for the ECG parameters QT interval, HR, QTcF interval, PR interval, and QRS complex will be summarized by treatment and time using sponsor reporting standards. Tables will be paged by parameter. Baseline is as defined in Section 3.5.4.

Mean changes from baseline in QT, heart rate and QTcF will be plotted against time postdose. On each plot there will be 1 line for each treatment, all treatments on the same plot including the placebo. Corresponding individual plots of changes from baseline will also be produced for each treatment.

In addition for QTcF, heart rate and QT, the differences between each dose and placebo (dose – placebo) will be summarized and plotted (N, mean, 90% CI) for each dose and timepoint (including baseline).

Changes from baseline in QTcF will be plotted separately against drug concentrations. This will be a scatter plot for all observations where QTcF and drug concentration are recorded. Placebo data will also be included (with drug concentration set to zero). Different symbols will be used for each treatment.

In addition, an attempt may be made to explore and characterize the relationship between plasma concentration and QT interval length using a PK/PD modeling approach. If a PK/PD relationship is found, the impact of participant factors (covariates) on the relationship may be examined. However, this analysis will not be presented in the CSR.

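### Part 1 ECG and vital signs: with the time-matched placebo reading as baseline, change on placebo is zero by construction, and unplanned readings and participants who leave before placebo have no stated baseline

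*SAP*

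**What the plan says.** **Definition of baseline.** For Part 1, SAP 3.5.4 defines the ECG baseline "as the average of the time-matched triplicate data obtained while on placebo [Part 1". For QTcF, protocol 9.4.5.2 measures change against "the average of the time-matched baseline triplicate values while on Placebo (in Part 1". SAP 3.5.3 sets the vital-sign baseline "as the time-matched data obtained while on placebo [Part 1], 0H assessment on Day 1 [Part 2". Protocol 8.2.3 says that, for the CSR, a "within-participant, time-matched assessment of each PF-07202954 dose relative to placebo, will be reported", so the ECG reference is the participant's own placebo period. During conduct, the same section uses a different QTcF baseline: the mean of the triplicate "collected before dose administration on Day 1 of each period".

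**Outputs built on it.** SAP 6.6.3 and 6.6.4 summarise change from baseline by treatment and time. The change plots carry placebo: "On each plot, there will be 1 line for each treatment, all treatments on the same plot including the placebo". For the plot of QTcF change against concentration, "Placebo data will also be included (with drug concentration set to zero". Categorical tables by treatment use the change classes of SAP Appendix 1. They count unplanned as well as planned post-dose readings, and the same holds for the extremes: "Maximum increase or decrease in vital signs will also be summarized; all planned and unplanned postdose timepoints will be included in these summaries". Dose-minus-placebo differences are requested separately at each time.

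**Leavers.** Protocol 7.1.1 withdraws a participant from study intervention for marked QTcF prolongation. Under protocol 7.1, a participant who stops study intervention for good does not stay in the study.

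**The concern.** The definition and the outputs do not fit together. A time-matched placebo reference suits a table of active doses only. Once placebo is itself a column, a line or a set of points in a change display, it is compared with itself. A reader takes a placebo column as a measure of background variation; here it cannot show any.

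Two gaps follow from the same definition:

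- An unplanned reading between scheduled times has no time-matched placebo value. The hourly repeat ECGs that protocol 8.2.3 requires after a QTcF rise can fall there.
- A participant who leaves before the placebo period has no reference for any active reading. A QTcF rise that itself led to withdrawal could then not be counted in the >60 msec change class.

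Safety and tolerability are the Part 1 primary endpoint, and protocol Table 1 lists delayed cardiac repolarization as a potential risk.

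**Working it through.** **1. Design count.** Protocol Table 5 has 8 sequences of 2 participants over 4 Periods, with one placebo Period per sequence.

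- Participants: 8 × 2 = 16.
- Placebo administrations: 16 × 1 = 16.
- Active administrations: 16 × 3 = 48.
- In each cohort and Period, 3 sequences × 2 = 6 active and 1 × 2 = 2 placebo. This reproduces the plan's own allocation of 6 active and 2 placebo per dose level.

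**2. Change from baseline.** Let A(t) and P(t) be a participant's readings at planned time t on an active dose and on placebo. The baseline at t is P(t).

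- Placebo change: P(t) − P(t) = 0 at every planned time, with SD 0.
- Active change: A(t) − P(t), which is already dose minus placebo. Subtracting the placebo change again alters nothing.

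Consequences for planned readings:

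- The placebo line is flat.
- All 16 placebo administrations fall in the QTcF increase class of at most 30 msec.
- None can reach the 30 mm Hg systolic or 20 mm Hg diastolic change classes.
- The placebo points on the QTcF-concentration plot all lie at (0, 0).

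**3. Active administrations before own placebo (Table 5).**

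| Dose | Before own placebo / active |
|---|---|
| 1 and 2 | 6/6 each |
| 3 and 4 | 4/6 each |
| 5 and 6 | 2/6 each |
| 7 and 8 | 0/6 each |

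Total: 2 × (6 + 4 + 2 + 0) = 24 of 48.

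| Leaves after Period | No placebo baseline | Active administrations lost, each |
|---|---|---|
| 1 | 12 of 16 | 1 |
| 2 | 8 of 16 | 2 |
| 3 | 4 of 16 | 3 |

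With no dropout nothing is lost. The documents give no dropout rate.

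**4. Illustration of the imbalance (assumed inputs).** The documents give no QTcF variability. I simulated no drug effect, 100,000 replicates per setting. The SD of the analysed QTcF value (the triplicate mean) was 4 to 10 msec, the between-period SD 3 to 6 msec, and there were 8 to 12 post-dose times. The quantity is the probability that the maximum QTcF increase exceeds 30 msec.

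| Baseline | Active | Placebo |
|---|---|---|
| Own time-matched placebo (as planned) | about 0.01% to 27% | 0 |
| Pre-dose value of each Period | 0 to about 12% | 0 to about 12% |

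A middle setting (SD 6, between-period SD 4, 10 times) gives about 1.5% on active with the planned baseline and about 0.2% in both columns with the pre-dose baseline. The top of the range needs SD 10 for the triplicate mean. If 10 msec is instead the SD of a single tracing with independent errors, the triplicate mean has SD 10/√3 = 5.8, and the 27% falls to about 4%. Rises above 60 msec stay at or below about 0.2% with either baseline.

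Steps 2 and 3 do not depend on these assumptions.

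**The case against.** The strongest reply is that the choice is deliberate. Protocol 8.2.3 gives two baselines for two purposes, and the time-matched placebo reference removes diurnal drift from the active contrasts. The placebo wording for the plots is shared with Part 2, where a placebo line is informative. Placebo still varies in the absolute summaries and in adverse events, and dose-minus-placebo differences are reported. All of this stands and limits the harm. It does not make the Part 1 placebo change column or line meaningful.

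Further points:

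- **Leavers.** The loss depends on dropout. Of the 24 administrations, 20 are at Doses 1 to 4 (6 + 6 + 4 + 4), planned as 10 to 300 mg. There the predicted Cmax is at most 310 ng/mL, about one-ninth of the nonclinical QTc no-effect level of 2770 ng/mL (2770/310 = 8.9). A marked rise may also be reported as an adverse event, and a value above 500 msec enters the absolute class. So the event need not vanish from the report, but it would be missing from the change table. Replacement under protocol 9.2 is optional, excludes safety discontinuations and gives the leaver no baseline.
- **Sponsor standards.** The CDISC Safety Rulebook and the sponsor's reporting and imputation standards may hold a fallback for unplanned readings and leavers. They are not in the documents, and the SAP states no rule. Such a fallback would not change the zero placebo column.
- **Vital signs.** SAP 3.5.3 does not say within-participant; own placebo is the natural reading. Protocol 4.2.2 pools placebo data for escalation decisions. Under a pooled baseline, individual placebo changes would not be zero and leavers would have a reference, but the mean placebo change would still be zero.
- **Noise.** A pre-dose baseline also puts the noise of two readings into each change. True, but it does so equally for placebo and active, which is what a side-by-side display needs.

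**Conclusion.** The concern holds and should be fixed. As written, the Part 1 change-from-baseline displays for ECG and vital signs put a placebo group that cannot vary at planned times beside active groups that can. This follows from the stated definition and the one placebo dose per participant. For ECG it rests on the within-participant rule in protocol 8.2.3; for vital signs it rests on reading the baseline the same way. The plan also states no baseline for unplanned readings or for participants who leave before placebo, a position that covers 24 of 48 active administrations should the participant leave at that point.

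The size of the resulting imbalance in the >30 msec class is uncertain, because it depends on assumed variability. Absolute values, adverse events, dose-minus-placebo summaries and the QTcF checks during conduct do not share the zero-placebo artefact, and no hypothesis test or stopping rule uses the affected outputs. Parts 2 and 3 use a 0H baseline and are not affected. Laboratory outputs were not part of this point.

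**What to change.** **Preferred change.** For Part 1 ECG and vital signs, use the 0H pre-dose value of each Period as baseline (the triplicate mean for ECG) in the change summaries, maximum-change and categorical tables, change plots and the QTcF-concentration plot. Keep the within-participant, time-matched comparison for the dose-minus-placebo summaries already planned in SAP 6.6.3 and 6.6.4. Align SAP 2.1, 3.5.3 and 3.5.4 with the note to protocol Table 2 and with protocol 8.2.3 and 9.4.5.2. The SAP 2.1 and Table 2 notes cover all non-PK endpoints, so limit the edit there to ECG and vital signs.

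**Smaller repair, if the placebo baseline is kept.** Label the active changes as placebo-adjusted and omit the placebo change column, line and points. State which baseline applies to an unplanned reading and to a participant with no placebo Period.

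**Cost.** Wording and programming only; pre-dose ECG and vital signs are already collected in every Period. The preferred change may need a protocol amendment, because both documents require one for major changes to the analysis of a primary endpoint. Its downside is that within-period changes keep diurnal drift, although the placebo column would then show that drift.

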## 4. ANALYSIS SETS (POPULATIONS FOR ANALYSIS)

For purposes of analysis, the analyses sets are defined as outlined in Table 6.

**TABLE 6. DEFINITION OF THE ANALYSES SETS IN STUDY C4171001**

Participant Analysis Set	Description
Enrolled/Randomly assigned to study intervention	"Enrolled" means a participant's agreement to participate in a clinical study following completion of the informed consent process and randomization: 
 
Potential participants who are screened for the purpose of determining eligibility for the study, but do not participate in the study, are not considered enrolled.
 

Evaluable	All participants randomly assigned to study intervention and who take at least 1 dose of study intervention for the given Part (1, 2, or 3).
Safety	All participants randomly assigned to study intervention and who take at least 1 dose of study intervention for the given Part (1, 2 or 3). Participants will be analyzed according to the product they actually received.
PK Concentration	All participants who receive at least 1 dose of PF-07202954 and in whom at least 1 PK concentration is reported, for the given Part (1, 2, or 3).
PK Parameter	All participants who receive at least 1 dose of PF-07202954 and who have at least 1 of the PK parameters of interest calculated, for the given Part (1, 2, or 3).

## 5. GENERAL METHODOLOGY AND CONVENTIONS

This is a 3-part sponsor-open study with Part 1 and Part 2 as investigator and participant blinded. Specific Pfizer personnel (analytical staff, medical monitor, clinical leads, clinicians, statistician, programmers, data managers and pharmacokineticists and people shadowing these team members) will be unblinded to participant treatments in order to permit real-time interpretation of the safety and PK data. Treatment randomization information will be kept confidential by Pfizer personnel and will not be released to the investigator/site staff until the conclusion of the study. Final analysis will follow the official database release after completion of all parts of the study.

### 5.1. Hypotheses and Decision Rules

There are no statistical hypotheses or decision rules.

### 5.2. General Methods

#### Descriptive Statistics

Descriptive statistics, including the sample size, mean, standard deviation, median, minimum, and maximum values, will be provided for continuous endpoints. For binary/categorical variables the number and proportion of participants achieving the thresholds will be presented. Some measures will be summarized using graphical representations by treatment and study day of visit, where appropriate.

#### Mixed Effect Analysis of Variance (ANOVA)

The mixed effect ANOVA model will be used to assess the food effect in Part 1 or Part 3, **CCI** For endpoints in Part 1 of the study treatment group will be the fixed effect and participant will be the random effect. In Part 3, sequence, period and treatment will be the fixed effects and participant within sequence will be the random effect. Estimates of treatment effects will be assessed using the least square means (LSMs) and 80% Confidence Intervals (CIs). Estimates of the mean differences between each active dose and placebo, and the corresponding 80% CI will be obtained from the model. If there are major deviations from the statistical assumptions underlying this model then non-parametric analyses may be presented.

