Given the current study is the first time PF-07202954 will be administered to humans, an escalating single oral dose design is planned with careful assessment and ongoing review of safety data and PK of PF-07202954. Part 1 is designed as a randomized, dose -escalating, cross-over, interleaving, placebo-controlled, 2-cohort, study with dosing of study intervention (PF-07202954/placebo) planned following ≥ 10 hours overnight fast, at approximately 8:00AM (± 2 hours) to occur **with** standard morning meal provided ~ 30 mins

prior to dosing at 0H. By design, at each dose level, 6 participants are planned to receive PF-07202954 and 2 participants are planned to receive placebo with all participants at the end of Part 1 having received 1 dose of placebo and up to 3 *unique* doses of PF-07202954. The rationale for selection of the starting (ie, first) dose level in Part 1 is outlined in [Section 4.3.3](#). In addition, the highest anticipated steady-state AUC₂₄ and C_{max} for PF-07202954 in Part 1 will *not* exceed the pre-identified stopping exposure limit determined based on nonclinical toxicity study (refer to [Section 6.6.1](#)) *nor* exceed the highest feasible total daily dose of 2000 mg.

The design of Part 1 permits both a within and between participant assessment of safety/tolerability and dose-response for PK and exploration of effect on plasma PCSK9. Furthermore, to permit an unbiased assessment of safety, the administration of active versus placebo in each Period will be double-blinded to both site staff (except those involved in preparation of doses) as well as the participants. However, to permit real-time review of the safety and PK data, the sponsor will be unblinded, although measures to limit degree of unblinding will be exercised – refer to [Section 9.5](#) for details. In light of the findings in the 6 week toxicity studies in rats and monkeys, the safety assessments envisioned in this study administrating investigational product for the first time to humans are outlined in [Section 8.2](#).

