For a given participant, dosing will be separated by **≥10 days**, with this planned dosing interval deemed sufficient based on the predicted PF-07202954 effective half-life of approximately 8 hours. In addition, this interval accounts for the required time for review of the safety, tolerability, and PK data from each dosing period before making a decision on the subsequent PF-07202954 dose to be evaluated. The planned doses in the escalation sequence (refer to [Table 3](#)) may be modified or repeated, as guided by emerging safety and PK data but will follow the dose-escalation rules defined in [Section 6.6.1](#). The data from participants as they receive placebo will be pooled and compared to data from each active dose to determine the next escalating dose of PF-07202954. The assessment of the full range of doses will require the planned 8 Periods of dosing (4 Periods per participant). In the event that additional dose-escalation is no longer warranted (eg, maximum tolerated dose identified, clear evidence of plateau in plasma PK based on observed data with at least 2 dose-levels), the additional periods in this 4-Period, cross-over design may be used to repeat a previously administered dose, study a lower and/or intermediate dose, and/or undertake an exploratory assessment of plasma PK with dosing following an overnight fast of **≥10 hours** *or* dosing following a high fat/high caloric morning meal (compared to dosing following a standard morning meal in previous Periods within the same cohort) to explore any potential food effect. And pending observed plasma PK data from Part 1, this study may also conduct Part 3 – refer to [Section 4.2.4](#) – to compare plasma PK following dosing in the fasted state (Reference) to dosing with a high-fat/high-caloric morning meal (Test).

4.2.3. Rationale for Part 2

[figure not shown]

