14. History of sensitivity to heparin or heparin-induced thrombocytopenia *only if* heparin is used to flush IV catheters used during serial blood collections.
15. Unwilling or unable to comply with the lifestyle considerations outlined in [Section 5.3](#).
16. *In Part 2 only*, participants meeting criteria for contraindication to undergoing imaging assessments including –
 - Active placement of medical devices in/on thoracic cavity as these interfere with use of ultrasound-based imaging modalities, and MRI;
 - History/evidence of any of the following:
 - Contraindication to MRI such as ferric implant;
 - History of severe claustrophobia impacting ability to perform MRI during the study even despite mild sedation/treatment with a *short-acting* anxiolytic;
 - Inability to lie still within the *closed* environment of the MRI scanner *or* maintain a breath hold for the required period to acquire images *even despite* mild sedation/treatment with an anxiolytic.
17. Investigator site staff or Pfizer employees directly involved in the conduct of the study, site staff otherwise supervised by the investigator, and their respective family members.

Randomization Criteria – Parts 1, 2, and 3

Participants will be randomized into the study provided they have satisfied **all** the following criteria:

- Eligibility criteria outlined in [Section 5.1](#) and [Section 5.2](#);
- *In addition*, prior to dosing on Day 1, the results of the clinical laboratory tests (including urine drug test) **conducted upon each inpatient admission** must be deemed to have no clinically significant findings, in the opinion of the PI, and as such permit (continued) participation in this study.

In Part 1, participants in the 2 cohorts will be randomized per the scheme summarized in Table 5 with the actual dose administered following the proposed dose-escalation approach outlined in [Section 4.3.3](#) and [Table 3](#).

Table 5. Study C4171001 - Part 1 - Randomization Scheme

Cohort	Sequence	Period ^a			
		1	2	3	4 ^b
1 (n=8)	1 (n=2)	Placebo	Dose 3	Dose 5	Dose 7 ^c
	2 (n=2)	Dose 1	Placebo	Dose 5	Dose 7 ^c
	3 (n=2)	Dose 1	Dose 3	Placebo	Dose 7 ^c
	4 (n=2)	Dose 1	Dose 3	Dose 5	Placebo ^c
2 (n=8)	5 (n=2)	Placebo	Dose 4	Dose 6	Dose 8 ^c
	6 (n=2)	Dose 2	Placebo	Dose 6	Dose 8 ^c
	7 (n=2)	Dose 2	Dose 4	Placebo	Dose 8 ^c
	8 (n=2)	Dose 2	Dose 4	Dose 6	Placebo ^c

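### The Part 1 mixed model has no period term although dose rises with period; for endpoints also measured on placebo, a period-adjusted run should be planned beside it

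*SAP*

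**What the plan says.** The mixed-model paragraph of SAP 5.2 gives the Part 1 terms as "For endpoints in Part 1 of the study treatment group will be the fixed effect and participant will be the random effect". The next sentence treats the other crossover differently: "In Part 3, sequence, period and treatment will be the fixed effects and participant within sequence will be the random effect". The output is described as "Estimates of the mean differences between each active dose and placebo, and the corresponding 80% CI will be obtained from the model". The stated use is "The mixed effect ANOVA model will be used to assess the food effect in Part 1 or Part 3"; the rest of that sentence is redacted.

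Protocol 4.2.2 describes Part 1 as a "cross-over, interleaving, placebo-controlled, 2-cohort, study", and at each dose level "6 participants are planned to receive PF-07202954 and 2 participants are planned to receive placebo". It adds: "The assessment of the full range of doses will require the planned 8 Periods of dosing (4 Periods per participant"). Under the randomization criteria in Protocol 5.2, "participants in the 2 cohorts will be randomized per the scheme summarized in Table 5". That table puts Doses 1, 3, 5 and 7 in Periods 1 to 4 of Cohort 1, and Doses 2, 4, 6 and 8 in Periods 1 to 4 of Cohort 2. Placebo moves through all four periods. No readable passage adds period to the Part 1 model.

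**The concern.** Because each dose occupies one period of its cohort and doses climb over time, dose and time move together. Without a period term, each dose is compared with placebo averaged over all four periods, so a change over time that has nothing to do with drug enters the dose contrast. Periods are at least 10 days apart and each involves confinement, standard meals and repeated blood sampling, so some drift in a marker is plausible, though no document gives evidence of it.

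A steady drift would look like a monotone dose trend. The design contains what is needed to check this: two placebo participants per cohort in every period. The model as written does not use them for that purpose. At stake is the reading of exploratory Part 1 endpoints that are also measured on placebo.

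**Working it through.** **Inputs.** The layout is Protocol Table 5: 8 sequences x 2 participants x 4 periods = 64 observations. Model terms and the 80% level are from SAP 5.2. The documents give neither the drift d nor the intra-participant correlation, so both are assumed: correlation 0.3 to 0.7, and d in units of within-participant SD.

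**Reproducing the plan's figures.** Counting cells gives 16 participants, 6 active and 2 placebo in each of the 8 cohort-periods, and 4 participants on both Dose 5 and Dose 7 (likewise Doses 6 and 8). These match the stated 16, 6 + 2, and the 4 in Table 5 footnote c.

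**Bias by hand (correlation 0).** The average period of a placebo observation is (1+2+3+4)/4 = 2.5. A dose given in period p is therefore biased by (p - 2.5)d, which is -1.5d, -0.5d, +0.5d and +1.5d.

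**Bias under the SAP model.** The estimator is (X'V⁻¹X)⁻¹X'V⁻¹y, with V compound-symmetric within participant. Setting y = d x period gives the bias in dose minus placebo:

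| Correlation | Doses 1-2 | Doses 3-4 | Doses 5-6 | Doses 7-8 | Dose 7 - Dose 1 | Dose 5 - Dose 1 |
|---|---|---|---|---|---|---|
| 0.3 | -1.583d | -0.528d | +0.528d | +1.583d | 3.17d | 2.11d |
| 0.5 | -1.607d | -0.536d | +0.536d | +1.607d | 3.21d | 2.14d |
| 0.7 | -1.622d | -0.541d | +0.541d | +1.622d | 3.24d | 2.16d |

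The last column applies to the six doses of Protocol Table 3 placed in Periods 1-3. If Period 4 is not run at all, that difference is 2.13d to 2.22d.

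**Adding period as a fixed factor.** The design has full rank (12 of 12 columns) and the bias is zero for every dose. Standard errors of dose minus placebo, in within-participant SDs:

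| Correlation | Without period | With period | Ratio |
|---|---|---|---|
| 0.3 | 0.505 | 0.711 | 1.41 |
| 0.5 | 0.519 | 0.737 | 1.42 |
| 0.7 | 0.532 | 0.757 | 1.42 |

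**Effect on the 80% interval for Dose 7 minus placebo.** With normal approximation and known variance, coverage is Φ(1.282 - b/SE) - Φ(-1.282 - b/SE). At correlation 0.5 and d = 0.25, b = 1.607 x 0.25 = 0.402 and b/SE = 0.402/0.519 = 0.774, giving about 67%. At d = 0.1 coverage is about 78%; at d = 0.5, about 39%.

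**When adjustment lowers mean squared error.** The drift must exceed √(SE²with - SE²without)/|bias per d|. At correlation 0.5 this is √(0.737² - 0.519²)/1.607 = 0.523/1.607 = 0.33 SD per period for the lowest and highest doses, and 0.523/0.536 = 0.98 for the middle doses.

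**Plasma PK.** Protocol 6.3.2 says placebo specimens are not routinely analysed, so only active periods contribute. With period added, the design on the Table 5 layout has 11 columns but rank 8: period is aliased with dose. A Dose 7 versus Dose 5 contrast then carries exactly 1.0d of drift, and no period term can remove it.

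**The case against.** The case against has substance.

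- The only use of the model that can be read is the food effect, a PK comparison for which a period term does nothing. This stands, and it limits the fix to endpoints measured on placebo.
- Primary and secondary Part 1 results do not depend on this model. SAP 5.1 has no hypotheses or decision rules, SAP 6.2 plans no formal inference on Part 1 plasma PK, and SAP 6.6 plans no formal analysis of standard safety data. This stands. A reader might infer that the main Part 1 conclusions are biased; the documents do not support that.
- Redacted text may list the endpoints or give a within-period baseline that would absorb slow drift. This stands as a limit. The default Part 1 baseline (note to SAP Table 2) is time-matched placebo data, which for any participant comes from a different period than the active dose, so it would not remove drift. That note allows deviations in SAP Section 3, part of which is redacted.
- The 3.2d figure assumes escalation through Period 4. Protocol Table 3 lists six doses, and Period 4 may repeat a dose, use a lower one or explore food (Protocol 4.2.2). This stands; hence the 2.1d alternative.
- Omitting period is a defensible trade of bias for precision with 6 participants per dose, and Protocol 4.2.2 itself pools placebo for escalation decisions. This stands against replacing the main model, but not against a second run beside it.

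**Conclusion.** The point holds for Part 1 endpoints measured on both active drug and placebo. As written, the model passes period drift into the dose contrasts: about -1.6d to +1.6d against placebo, and about 3.2d from lowest to highest dose (2.1d for six doses in Periods 1-3). This assumes linear drift common to both cohorts, the Table 5 layout, and correlation 0.3 to 0.7. The real d is unknown, and at 0.1 SD per period the interval is barely affected.

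Two stronger readings are tempting. One is that a period term would also rescue a Part 1 food comparison. It would not, because that comparison is aliased with period. The other is that the period-adjusted estimates must become the main result. That would be a gain in mean squared error for the extreme doses only if drift exceeds about 0.33 SD per period, and for the middle doses only near 1 SD.

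With no hypothesis tests, exploratory endpoints and a redacted endpoint list, this is a minor to moderate point: a cheap improvement to the plan.

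**What to change.** In SAP 5.2, prespecify a second version of the Part 1 mixed model with period as a fixed effect, for endpoints measured on both active drug and placebo. Report its dose-minus-placebo estimates and 80% intervals beside those of the main model, so that a reader can see whether an apparent dose trend survives adjustment. The cost is one extra model run; it needs no new data and no design change. The downside is standard errors about 42% larger in that run.

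For plasma PK, do not rely on a period term. State in the SAP that, if Period 4 of Part 1 is used for fasted or high-fat dosing, food and period cannot be separated on the Table 5 layout, and keep that result exploratory, as Table 5 footnote b already describes it.
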